3.5. HFNC treatment

HFNC will be initiated at 50 L/min (AIRVO2 or Optiflow, Fisher &Paykel Health care Limited., Auckland, New Zealand) with temperature set at 37 °C. Nasal cannula size should be \leq

50% of the patient's nostril size. $F_{I}O_2$ will be adjusted to maintain SpO_2 at 90% to 95%. Flow and temperature will be adjusted based on patient's comfort and clinical response. Patients' vital signs, SpO_2 , oxygen device and $F_{I}O_2$ before HFNC will be recorded, Patients' vital signs, SpO_2 , HFNC flow and $F_{I}O_2$ at 30 mins, and 2 hour of HFNC will also be recorded for both groups. HFNC will be continuously delivered after enrollment in the study for ≥ 16 hours a day in the first 3 days. Patient comfort to HFNC, will be assessed by means of a scale used and validated in previous studies that is defined as follows: 1, bad; 2, poor; 3, sufficient; 4, good; 5, very good. Patients' vital signs, SpO_2 , HFNC flow and $F_{I}O_2$, as well as patient comfort will be documented every 4-6 hours. In order to prevent virus transmission, all the patients with HFNC treatments will wear a surgical mask over the face.¹⁶

3.6. Withdraw criteria

- 1) Patients cannot tolerate HFNC or prone position for 30 mins
- 2) Patients experience any side effects during prone position, including vomit, dizzy, hypotension, etc.

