3.8 Treatment Failure Criteria

Failure criteria: treatment failure is defined as one of the following criteria¹⁷:

(1) Signs of persisting or worsening respiratory failure, defined by at least two of the following criteria:

- Respiratory rate above 40 cycles/min
- Lack of improvement of signs of respiratory-muscle fatigue
- Development of copious tracheal secretions
- Respiratory acidosis with a pH below 7.35
- SpO₂ below 90% at F_IO₂ ≥ 0.8 for more than 5 min without technical dysfunction

(2) Hemodynamic instability defined by a SBP below 90 mmHg, MBP below 65 mmHg or requirement for vasopressor;

(3) Deterioration of neurologic status (with a Glasgow coma scale below 12 points).

For patients who meet the failure criteria in the HFNC and HFNC+PP groups, a trial of NIV might be allowed according to the physician's preference in patients with signs of persisting or worsening respiratory failure and no other organ dysfunction before performing endotracheal intubation and invasive ventilation. Reasons for intubation will be recorded as well.

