3.8 Primary endpoint

28 days after randomization.

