4. CHARACTERISTICS OF DATA/SPECIMENS TO BE ANALYZED

4.1. Data collection

The following information of all patients is collected in a data file: patients' characteristics, including age, gender, medical history, diagnosis for COVID-19, the laboratory and microbiology findings, treatment and outcome. Complications including skin breakdown, IV line or nasal cannula dislodgement or desaturation during position change. The respiratory assessments before, during the treatments of HFNC or HFNC with prone position.

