4.2. Statistical analysis

Definition of the two groups: The patients who receive the prone positioning are classified as prone positioning group. The patients who receive HFNC alone are classified as HFNC group.

Comparisons between the two groups: Quantitative continuous variables are given as either means (\pm SDs) or medians (with inter-quartile ranges) are compared using the unpaired Student's t test or the Mann-Whitney test. Qualitative or categorical variables are compared with the chi-square test or the Fisher's exact test. ANOVA for paired tests to compare the same variables collected at different time points are used. The cumulative probability of remaining on spontaneous breathing are compared with the Kaplan-Meier estimate of survival and the log-rank test to compare the two groups. Univariate and multivariate analyses of risk factors for PP failure

are performed with logistic regression. All analyses are in intention to treat, and the level of significance is set at 0.05.

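### Section 4.2 defines the comparison groups by treatment received, which conflicts with its own intention-to-treat sentence and with the randomised arms in 3.2

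*Combined protocol and SAP*

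**What the plan says.** Section 3.2 forms two arms by central randomisation, stratified by ARDS severity: prone positioning (PP), and a control arm on HFNC without proning.

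Section 4.2 then opens with its own labelled definition of the groups: "The patients who receive the prone positioning are classified as prone positioning group", and "The patients who receive HFNC alone are classified as HFNC group". It closes with "All analyses are in intention to treat, and the level of significance is set at 0.05". It defines no intention-to-treat set, does not say which rule governs when they differ, and does not say how much proning counts as having received it.

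Section 3.6, Withdraw criteria, has two items: "Patients cannot tolerate HFNC or prone position for 30 mins" and "Patients experience any side effects during prone position, including vomit, dizzy, hypotension, etc". It does not say whether such a patient leaves the session, the assigned treatment or the trial. As allocated, the second item and the prone half of the first can arise only in the PP arm. The HFNC half can arise in either arm.

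Three other places bear on this. Section 4.1 says "The following information of all patients is collected in a data file", and its list includes treatment and outcome. The primary endpoint is timed at "28 days after randomization". The failure definition ("treatment failure is defined as one of the following criteria") makes no exception for patients who have met 3.6.

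**The concern.** Grouping by what was received and grouping as randomised agree for every patient who follows the allocation. They part company for those who do not, and those are the patients for whom an intention-to-treat rule exists.

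Not starting PP may be related to prognosis. A patient allocated to PP who is intubated before the first session has received HFNC alone. By the receipt rule that event counts against the control group. A patient who improves before the first session would shift the comparison the other way. A control who turns prone unprompted moves into the PP group. Self-proning is foreseen by the protocol, since exclusion criterion 11 concerns it, but nothing says how a control who does it after randomisation is classified.

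At stake is whether the intubation and treatment-failure comparison remains the randomised one. Assignment is unblinded (section 3.3), so who prones is decided with the allocation known.

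**Working it through.** **Classification under each rule**

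| Patient | 3.2 with intention to treat | 4.2 by receipt |
|---|---|---|
| Allocated PP, prones as planned | PP | PP |
| Allocated PP, prones, then stops for a side effect | PP | PP (no minimum exposure given) |
| Allocated PP, never prones | PP | HFNC alone |
| Allocated control, never prones | Control | HFNC alone |
| Allocated control, self-prones | Control | PP |

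The rules conflict in rows 3 and 5. Row 2 is unclear only because no minimum exposure is set.

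**Inputs from the plan (4.2, 4.3).** Intubation 60% with HFNC and 45% with PP; significance level 0.05; power 80%; total 346. Equal allocation is assumed: there are two arms and a block length of 4, but no ratio is stated.

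**The plan's own figure.** Two-sided test of two proportions, pooled variance, no continuity correction:

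n per arm = [1.96·√(2·0.525·0.475) + 0.8416·√(0.60·0.40 + 0.45·0.55)]² / 0.15² = 172.8, so 173 per arm and 346 in total. This reproduces.

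**Assumptions not in the documents.** A share w of the PP arm never prones, and these patients have intubation risk r. There is no true effect, so each randomised arm has 60%. For this illustration no control self-prones.

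**Formulas.**
- PP group by receipt: (0.60 − w·r)/(1 − w), on 173(1 − w) patients.
- HFNC group by receipt: (0.60 + w·r)/(1 + w), on 173(1 + w) patients.
- False-positive rate favouring PP: Φ(difference/SE − 1.96), with SE ≈ √[0.6·0.4·(1/n₁ + 1/n₂)] = 0.0527 in the cases below.

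**w = 0.02, r = 0.75.** PP: (0.60 − 0.015)/0.98 = 0.5969 on 169.5. HFNC: (0.60 + 0.015)/1.02 = 0.6029 on 176.5. Difference 0.6 points; Φ(0.114 − 1.96) = 3.2%.

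**w = 0.03, r = 0.75.** PP: (0.60 − 0.0225)/0.97 = 0.5954 on 167.8. HFNC: (0.60 + 0.0225)/1.03 = 0.6044 on 178.2. Difference 0.9 points; Φ(0.171 − 1.96) = 3.7%.

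**Other values of r.** At r = 0.60 there is no bias and the rate is 2.5%. At r = 0.50 the difference reverses: 0.4 points against PP for w = 0.02 (0.6020 v 0.5980) and 0.6 points for w = 0.03 (0.6031 v 0.5971). The chance of a false result against PP is then 3.0% and 3.2%.

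**Self-proning controls.** The same formulas apply with the arms exchanged. Controls with below-average risk who move into the PP group favour PP; those with above-average risk count against it.

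**Analysed as randomised.** Both arms stay at 60% on 173 each, and the rate is 2.5% for every w and r.

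**The case against.** The strongest reply is that the 4.2 sentences only label arms that 3.2 has already defined by allocation. They reuse the name of the PP arm, and the intention-to-treat sentence covers all analyses without exception. That is probably what was meant. But the text is presented as the definition of the two groups and turns on receipt, so a statistician who applied it literally would be following the plan.

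A second reply is that few patients can move. Section 2.2 excludes those who refuse or cannot cooperate with HFNC or PP, who have a contraindication to PP, or who cannot communicate. This stands, and it is why the illustration uses 2–3%.

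A reader might infer two stronger versions. Neither is supported.

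- **Every patient who stops PP is counted as HFNC alone.** With 10% stopping at 75% risk this would give 3.0 points and an 8.3% false-positive rate. But anyone with a side effect while prone has received PP and literally stays in the PP group. Only very short exposure is ambiguous.
- **Section 3.6 removes patients from the trial.** With 10% dropped at 75% risk this would give 1.7 points and 4.9%. But 3.4 treats tolerance as a matter for the session, 4.1 collects outcomes for all patients, and the day-28 endpoint has no exception. Duration, comfort and complications of PP are planned outcomes (1.4), which would make little sense if these patients left. The intention-to-treat sentence would also have to be ignored.

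**Conclusion.** The group definition in 4.2 is wrong as written. It contradicts the intention-to-treat sentence in the same section and the arms in 3.2, and following it would break the randomised comparison for PP patients who never prone and controls who do.

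The likely effect is small: under the stated assumptions, below 1 point against a planned 15 and about 1 percentage point of excess one-sided error. The 2–3% share and the 75% risk are illustrative. The effect can run either way, and it would be larger if the missing exposure threshold led early stoppers to be moved too. If the analysis follows allocation, there is no bias.

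The silence of 3.6 is a secondary matter. It needs a clarifying sentence, and it is not evidence that patients who stop PP will be lost or excluded.

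**What to change.** In 4.2, replace the definition by receipt with groups as randomised: every patient is analysed in the allocated arm, whatever proning takes place. If an as-treated comparison is wanted, label it supplementary and state the minimum exposure that counts as PP.

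As a supporting clarification in 3.6, state that meeting a criterion ends the prone session or the assigned treatment only, and that every randomised patient is followed to day 28 unless consent is withdrawn. Whether a given side effect should stop proning remains a clinical decision for the investigators.

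The cost is a wording amendment to two sections. Outcome collection for these patients is already implied by 4.1 and the intention-to-treat sentence, so little is added, although the documents do not state the effort needed to reach day 28. N = 346, eligibility and treatment do not change.

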3.7 Weaning criteria

- 1) Patients' $PaO_2/F_{I}O_2 > 300$ mmHg, or $SpO_2/F_{I}O_2 > 340$

3.8 Treatment Failure Criteria

Failure criteria: treatment failure is defined as one of the following criteria¹⁷:

(1) Signs of persisting or worsening respiratory failure, defined by at least two of the following criteria:

- Respiratory rate above 40 cycles/min
- Lack of improvement of signs of respiratory-muscle fatigue
- Development of copious tracheal secretions
- Respiratory acidosis with a pH below 7.35
- SpO₂ below 90% at F_IO₂ ≥ 0.8 for more than 5 min without technical dysfunction

(2) Hemodynamic instability defined by a SBP below 90 mmHg, MBP below 65 mmHg or requirement for vasopressor;

(3) Deterioration of neurologic status (with a Glasgow coma scale below 12 points).

For patients who meet the failure criteria in the HFNC and HFNC+PP groups, a trial of NIV might be allowed according to the physician's preference in patients with signs of persisting or worsening respiratory failure and no other organ dysfunction before performing endotracheal intubation and invasive ventilation. Reasons for intubation will be recorded as well.

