The early application of PP with HFNC, especially in patients with moderate ARDS and baseline $SpO_2 > 95\%$, may help avoid intubation. In a preliminary study, PP was well tolerated with noninvasive respiratory supports, and the efficacy in terms of PaO_2/FiO_2 with HFNC + PP was higher than HFNC alone. Severe ARDS patients were not appropriate candidates for HFNC/NIV+PP, and a risk for delayed intubation should be noticed. A prospective RCT is warranted in the future in non-intubated moderate ARDS patients on the true benefits of PP before intubation.⁹

Coronavirus disease 2019 (COVID-19) is an emerging infectious disease that was first reported in Wuhan, China, and had subsequently spread worldwide, including in United States. Twenty-nine percent of COVID-19 patients may develop ARDS, 30% of these ARDS patients could be successfully supported with HFNC or NIV, and 60% of the ARDS patients needed intubation and invasive mechanical ventilation, or even ECMO support¹⁰.

Based on the potential beneficial mechanisms of HFNC and PP mentioned above, early use of PP combined with HFNC to avoid the need for intubation in COVID-19 patients with moderate to severe ARDS needs to be further investigated.

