1.2. Hypothesis / Key Questions

We hypothesize that early use of PP combined with HFNC can avoid the need for intubation in moderate to severe ARDS patients. The purpose of this RCT will be to evaluate the effects of PP combined with HFNC for improving oxygenation and reducing the need for intubation

compared with HFNC support alone, as well as the safety of the PP therapy in non-intubated COVID-19 induced ARDS patients.

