1.3. Primary Objectives

The primary outcome for the efficacy of PP combined with HFNC will be the treatment failure rate and intubation rate of HFNC or HFNC+PP support and clinical requirement for advanced respiratory support including NIV, invasive ventilation or ECMO.

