3.3. Blinding and Quality Control

The trial will be overseen by a steering committee, and data quality control will be completed by independent data monitoring board. Clinicians and epidemiologists of above organization are not members of participating in our research group. Research coordinator will timely verify database and regularly monitored all the centers on site to ensure the accuracy of

the data recorded. An investigator at each center is responsible for enrolling patients in the study, ensuring adherence to the protocol, and completing the electronic case-report form. Although the individual study assignments of the patients could not be blinded, the coordinating center and all the investigators will remain unaware of the study group outcomes until the data are unlocked. All the analyses are performed by the study statistician not involved in study recruitment, and blind of randomization group until database lock.

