4.3. Sample size calculation

Sample size estimation: Base on the intubation rate for COVID-19 induced ARDS patients reported in previous studies from 40% to 77%¹⁸⁻²⁰, we estimate at least a total of 346 subjects with an expected intubation rate of 60% in the moderate to severe ARDS patients with HFNC support, and of 45% [$80\% * (1-0.25)=45\%$, a 25% reduction] in the PP patients in our cases, with a confidence level $(1-\alpha)=95\%$ and power level $(1-\beta)=80\%$.

References

5. Kallet RH. A Comprehensive Review of Prone Position in ARDS. *Respir Care.* 2015;60(11):1660-1687.

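### The primary outcome lists several different events with no order or multiplicity rule, while the 346 patients and their 80% power apply to intubation alone.

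*Combined protocol and SAP*

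**What the plan says.** All references are to the combined protocol and SAP.

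- **Section 1.3** gives as primary the rate of treatment failure, the rate of intubation, and "clinical requirement for advanced respiratory support including NIV, invasive ventilation or ECMO". It does not rank these or combine them into one event.
- **Section 3.8, Treatment Failure Criteria**, defines failure by respiratory, haemodynamic or neurologic signs. Intubation is not needed to meet it. For patients who have met the criteria, "a trial of NIV might be allowed according to the physician's preference in patients with signs of persisting or worsening respiratory failure", in either arm, provided no other organ is failing.
- **Section 3.8, Primary endpoint**, consists only of "28 days after randomization".
- **Section 4.2** lists tests by type of variable and adds a time-to-event comparison: "The cumulative probability of remaining on spontaneous breathing are compared with the Kaplan-Meier estimate". No test is called primary, and the text does not say whether starting NIV ends that state.
- **Section 4.3** sizes the trial on intubation: "we estimate at least a total of 346 subjects with an expected intubation rate of 60" per cent on HFNC alone against 45% with prone positioning, at 80% power.
- **Section 1.2** states the aim as "improving oxygenation and reducing the need for intubation".

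**The concern.** A patient who meets the failure criteria, is given NIV and recovers counts as a treatment failure and as needing advanced support, but not as an intubation. A patient who fails on blood pressure or consciousness may likewise never be intubated. The components of section 1.3 are therefore different outcomes and can give different results on the same data.

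Two consequences follow. First, the 80% power belongs to intubation only; no rates, sample size or power are given for the other components. Second, a plan with several primary comparisons, each at 0.05 and with no rule linking them, does not hold the overall error rate at 5%. The statistician is "blind of randomization group until database lock", so an event left open until then would be settled with the allocation known.

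**Working it through.** **1. The plan's own figure.** Inputs from section 4.3: p₁ = 0.60, p₂ = 0.45, power 80%, α = 0.05. Two-sided testing and 1:1 allocation are not stated there; both are inferred because they reproduce the total. With mean rate p̄ = 0.525,

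n per arm = [1.96·√(2p̄(1−p̄)) + 0.8416·√(p₁(1−p₁) + p₂(1−p₂))]² / (p₁−p₂)² = 172.8, rounded up to 173, **total 346**.

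This is an exact match. (The bracket in section 4.3 prints 80% where 60% is needed: 60% × 0.75 = 45%. The slip does not affect 346.)

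**2. False-positive rate if two events are tested.** Assume no effect of proning, 173 per arm and 60% intubated in both arms. Let a further x points in each arm have NIV without intubation; x is assumed. Because every intubation is also a wider event (NIV, intubation or ECMO), the two test statistics have correlation √[0.60(0.40−x) / (0.40(0.60+x))]. Pooled z-tests were simulated in 1,000,000 trials per row:

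| x (points) | Correlation | Either event significant, two-sided | Either event significant in favour of proning |
|---|---|---|---|
| 5 | 0.90 | 7.1% | 3.6% |
| 10 | 0.80 | 7.9% | 4.0% |
| 15 | 0.71 | 8.5% | 4.3% |

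The nominal values are 5% and 2.5%. Intubation alone, tested in favour of proning, gives 2.6% in the same simulation. Two independent tests would give 1 − 0.95² = 9.75%, so the correlation limits the inflation but does not remove it. At x = 0 these two events coincide. Treatment failure under section 3.8 could still differ from both, and testing it as well could only raise the rate.

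**3. Power of 346 for the wider event.** Keep intubation at 60% v 45% and add x points of NIV-only controls. The prone-arm rate depends on what proning does to NIV-only cases, which the plan does not say. Two assumptions, same formula as step 1:

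| x | Proning cuts NIV-only cases by 25% | Power | N for 80% | Same share of never-intubated patients gets NIV in both arms | Power | N for 80% |
|---|---|---|---|---|---|---|
| 5 | 65% v 48.75% | 87% | 290 | 65% v 51.9% | 70% | 442 |
| 10 | 70% v 52.5% | 92% | 242 | 70% v 58.75% | 59% | 568 |
| 15 | 75% v 56.25% | 96% | 200 | 75% v 65.6% | 48% | 744 |

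In the second case the share is x/40 (12.5%, 25%, 37.5%), so the prone-arm rate is 45 + 55·(x/40). Power lies above 80% under one assumption and below it under the other.

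**4. How often the two events disagree.** In simulation under the rates of step 3, one event is significant for proning and the other is not in 10%, 15% and 18% of trials (first assumption) and in 14%, 25% and 35% (second).

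**The case against.** The strongest reply is that the plan already leans towards intubation. Section 1.2 aims at it, section 4.3 is sized on it, section 1.3 names it, and the treatment failure section asks for the reasons for it to be recorded. A patient on NIV is ordinarily still breathing spontaneously, so the survival curve in section 4.2 may well mean freedom from intubation. This stands as a reason to choose intubation in the fix. It does not settle the text, because section 1.3 gives the other components equal standing and no section says which one decides the trial.

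A second reply is that the sizes above rest on invented NIV rates. That is correct. The introduction reports that "30% of these ARDS patients could be successfully supported with HFNC or NIV", but it does not divide that figure between the two supports, and it describes a background population rather than patients already on HFNC who pass these exclusions. It supplies neither an estimate nor a bound. The ambiguity itself needs no assumed rate.

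A third reply is that nothing in the plan proposes choosing the event after unblinding. That is also correct. The inflation in step 2 does not need it: it follows from testing both events at 0.05.

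A reader might also infer that rescue NIV biases the trial in a known direction. The documents do not support this. Unequal unblinded use could shift intubation, but neither its size nor its direction can be derived, and NIV given after failure leaves the failure and advanced-support components unchanged.

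**Conclusion.** The concern holds as a defect in defining the primary event. Section 1.3 names several events that can diverge, no section ranks them or assigns a test, and the stated 80% power belongs to intubation alone. Testing intubation and the NIV-inclusive event each at two-sided 0.05 gives a false-positive rate of about 7 to 8.5%, if 5 to 15 in 100 controls have NIV without intubation, intubation is 60% in both arms, and 173 patients are in each arm. About half of those errors favour proning (3.6 to 4.3%, against 2.5%), so the larger figure should not be read as the rate of false claims of benefit.

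A reader might conclude that 346 is too few. The documents do not show that: 346 is right for intubation, and for the wider event its power could lie on either side of 80%. Nor is rescue NIV the only cause. Haemodynamic and neurologic failure would separate the events even if NIV were not allowed.

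**What to change.** 1. In sections 1.3, 3.8 (Primary endpoint) and 4.2, name intubation within 28 days of randomization as the only primary event, and tie one named test to it. This agrees with sections 1.2 and 4.3, so 346 and its power stand.
2. In section 4.2, state that NIV alone does not end the spontaneous-breathing state in the Kaplan-Meier analysis. State also how death without intubation is counted, for example as an event in a sensitivity analysis.
3. Make treatment failure as defined in section 3.8, and the composite of NIV, intubation or ECMO, secondary outcomes.
4. Report rescue NIV by arm.

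The cost is a few sentences and recording of NIV use; no patients are added. The downside is that intubation alone stays open to unequal unblinded use of rescue NIV. The secondary composite and the report by arm help to show this but do not remove it.

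If the sponsor prefers the wider event as primary, section 4.3 must give its assumed rates in both arms and the power of 346 for it. Under the assumptions in step 3 that choice needs from no extra patients up to 398 more (744 − 346). It also makes an unblinded bedside decision part of the primary outcome.
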